7.3 Missing Data

Missing data will not be imputed for any outcomes in this study and will be handled by means of direct likelihood analyses.

7.4 Statistical Methods

For all outcomes, summary statistics appropriate to the distribution will be tabulated on a subject level overall and within the subgroups defined in Section 12. For the CGM metrics, summary statistics appropriate to the distribution also will be tabulated for each 4-week interval and for the first and last 26 weeks of the study. For the questionnaires, summary statistics will be reported for the mean scores in addition to the individual responses for each question.

For all outcomes, a linear mixed model with a random subject effect will be used to test whether the mean change from baseline significantly differs from zero. These models will be fit for each of the subject level CGM metrics and HbA1c at 13, 26, 39, and 52 weeks. They also will be fit for the questionnaires at 26 and 52 weeks. If values are skewed, then winsorization will be utilized. Point estimates and 95% confidence intervals for change in glycemic outcomes will be reported.

For the three mental health screening questionnaires, only summary statistics will be tabulated. The three mental health screening questionnaires falling under this umbrella are the Patient

187 Health Questionnaire-8, the Diabetes Distress Scale (Management Distress Subscale), and the
188 Fear of Hypoglycemia Survey (Worry Subscale).

189 **7.5 Analyses Windows**

190 For HbA1c, only measurements occurring within ± 45 days of the target measurement date at a
191 given time point will be included in the tabulation of summary statistics. The windows for
192 glycemic metrics were defined above in Section 7.1.

193 **7.6 Sensitivity Analyses**

194 For CGM and HbA1c outcomes, a complete-case analysis restricting to non-missing outcomes
195 will also be assessed. A paired t-test (for normally distributed outcomes) or a Wilcoxon signed
196 rank test (for skewed outcomes) will be used.

197 **8 Safety Analyses**

198 All adverse events that occur on or after the date of enrollment will be listed in a table.

199 For events occurring on or after the date of CGM initiation, the reported safety outcomes include
200 diabetic ketoacidosis (DKA), severe hypoglycemia (SH), hospitalization, and emergency room
201 visits. The following statistics will be tabulated for each safety outcome:

- 202 • Total number of events
- 203 • Number and proportion of subjects with an event (discretized into bins)
- 204 • Incidence rate per 100 person years

205
206 The number of person-years for the incidence rate calculations will be inclusively defined as the
207 number of person-years in between the CGM initiation date and the last day of study follow-up
208 (completion date, withdrawal date, etc.).

209 **9 Adherence and Retention Analyses**

210 **9.1 Protocol Adherence**

211 The number of and reasons for participant contacts with the virtual clinic will be reported in a
212 table to assess protocol adherence for the study.

213 **10 Baseline Descriptive Statistics**

214 Baseline demographic and clinical characteristics of the cohort of all subjects who initiate the
215 CGM and were included in the glycemic analyses will be summarized in a table. Use of
216 medications and non-insulin therapy will also be reported. For continuous variables, summary
217 statistics appropriate to the distribution will be given. For discrete variables, number and
218 percentage will be reported for each category. Summary statistics for demographics and clinical
219 characteristics will be presented overall, by diabetes type, by insulin modality, by whether the
220 participant was seeing an endocrinologist or a primary care provider at baseline, by baseline
221 HbA1c groups ($<7.5\%$, 7.5% to $<9.0\%$, and $\geq 9.0\%$), and by age (<25 , $25\text{-}65$, and >65 years). Cut
222 points for age and baseline HbA1c may be reassessed after data are collected.

223 **11 Planned Interim Analyses**

224 No formal interim analyses or stopping guidelines are planned for this study. Data will be
225 monitored on an ongoing basis including:

- 226 • Status of enrolled participants
- 227 • Recruitment rates by month and by site
- 228 • Baseline demographic and clinical characteristics
- 229 • Dropped participants and reasons for discontinuing
- 230 • Reportable adverse events

231 **12 Subgroup Analyses**

232 Subgroup analyses for % of time using the CGM, % time in range, % time >180 mg/dL, % time
233 <70 mg/dL, and HbA1c will be performed based on the following factors:

- 234 • Baseline HbA1c (categorized as <7.5%, 7.5% to <9.0%, and ≥9.0%)
- 235 • Insulin modality
- 236 • Age (categorized as <25, 25-65, and >65)
- 237 • Type of healthcare provider (endocrinologist or primary care provider)
- 238 • Diabetes Duration (categorized as <5, 5-<10, 10-<20, ≥20)
- 239 • Race/Ethnicity
- 240 • Household income (categorized as <\$50,000, \$50,000-<\$100,000, and ≥\$100,000)

241 For continuous variables, results will be displayed in subgroups based on cut points although the
242 analysis will utilize the variable as continuous. Cut points for age, baseline HbA1c, diabetes
243 duration, and household income may be reassessed after the data are collected.

244 Within each subgroup, summary statistics will be tabulated. P-values for change from baseline
245 will be calculated within each subgroup using a linear mixed model will be performed as
246 described in Section 7.4.

247 Percentage of CGM discontinuations will also be tabulated by the factors listed above.

248 **13 Multiple Comparisons**

249 No adjustments for multiple comparisons will be made.

250 **14 Additional Analyses**

251 CGM metrics over 13-week periods will be tabulated on a subject level by time of day. In these
252 analyses, daytime will be defined as 6:00 AM to <12:00 AM and nighttime will be defined as
253 12:00 AM to <6:00 AM. For this analysis, CGM metrics will only be calculated if the participant
254 has at least 126 hours of CGM data during daytime and at least 42 hours of CGM data during
255 nighttime.

256 Total scores for questionnaires in Section 7.2 will be stratified by number of mental health
257 service sessions. Additional analyses will be conducted to assess the bivariate relationship
258 between questionnaire responses and glycemic metrics at 26 and 52 weeks. These relationships
259 will be assessed by displaying scatterplots, along with the corresponding Spearman correlation

260 coefficient. A 95% confidence interval for the Spearman correlation coefficient will be reported.
261 In these analyses, the following relationships will be explored:

262 • % Time <70 mg/dL vs. Fear of Hypoglycemia Worry Subscale Mean Score
263 • % Time <70 mg/dL vs. Hypoglycemia Confidence Survey Mean Score
264 • % Time in Range vs. Glucose Monitoring Satisfaction Survey Mean Score
265 • % Time in Range vs. Diabetes Distress Scale Management Distress Subscale Mean Score
266 • CGM use at 26 weeks vs. Diabetes Technology Attitudes Survey Mean Score

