### 452      **6.5 Analysis of Efficacy Outcomes**

453      CGM metrics and HbA1c will be calculated and summarized at 13, 26, 39, and 52 weeks.  
454      Summary statistics for questionnaires will be provided at all time points when they are collected.

455 A linear mixed model with a random subject effect will be used to assess whether the change  
456 from baseline significantly differs from zero. If values are highly skewed, then the winsorized  
457 mean will be tested or a transformation utilized. A complete-case analysis using a paired t-test or  
458 Wilcoxon signed rank test will also be assessed.

459 **6.6 Subgroup Analyses**

460 Subgroup analyses for HbA1c and selected CGM outcomes will be performed by baseline  
461 HbA1c group, insulin delivery modality, age, healthcare provider (endocrinologist or primary  
462 care provider), and various participant characteristics as described in the SAP.

463 **6.7 Safety Analyses**

464 All adverse events that occur post enrollment will be listed in a table. Additionally, each of the  
465 following safety metrics will be tabulated for reported SH and DKA events, hospitalizations and  
466 emergency room visits:

467     • Number of subjects with  $\geq 1$  event  
468     • Number of events per subject  
469     • Incidence rate per 100 person-years

470 **6.8 Baseline Descriptive Statistics**

471 Baseline demographic and clinical characteristics of the cohort of all subjects who initiate the  
472 CGM will be summarized in a table.

473 **6.9 Multiple Comparisons/Multiplicity**

474 No adjustments for multiple comparisons will be made.

475 **6.10 Additional Analyses**

476 Several additional analyses will be performed in this study. These will include the following:

477     • Tabulations of CGM glycemia and CGM use by month and comparing the first 26 weeks  
478 and last 26 weeks of the study (overall and within subgroups)  
479     • Tabulations of CGM glycemia by time of day  
480     • Tabulations of the number of participant contacts with the virtual clinic  
481     • Bivariate relationship between questionnaires and glycemic metrics following CGM  
482 initiation

483 **Chapter 7: Ethics/Protection of Human Participants**

484 **7.1 Ethical Standard**

485 The investigator will ensure that this study is conducted in full conformity with Regulations for  
486 the Protection of Human Participants of Research codified in 45 CFR Part 46, 21 CFR Part 50,  
487 21 CFR Part 56, and/or the ICH E6.

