TARGET WINDOW		Within 7 Days from Completion of Enrollment Questionnaires		Day 0	Day 7-14	Day 21-28		Weeks 12-14		
ICF • Eligibility Confirmation	X								X*	X*
Baseline Data Collection • Contact Information • Demographics • Medical History • Questionnaires	X		X							
Follow-Up Data Collection**					X	X	X	X	X	X
HbA1c***			X					X	X	X
Video Tutorials / Access to Resource Materials		Examples: CGM Overview Parts of CGM	Examples: HbA1c Sample Collection CGM Setup	Examples: Understanding Your Real-Time Data How to Change Sensor	Examples: How to Upload CGM Data How to View Reports Understanding Your Ambulatory Glucose Profile / Data Patterns	X	X	X	X	
Contact with Study Team [†]		X	X	CGM Initiation	CGM Data Interpretation	CGM Data Review Goal Setting	X	X	X	
CGM Use ^{††}			~2 Week Blinded CGM Use	Start of 26-Week Unblinded CGM Use	X	X	X	X	X	

*Virtual Clinic Training and Follow up phase ends at 26 weeks. Participant will be asked to extend follow up for an additional 26 weeks and sign an addendum ICF if they plan to continue to use CGM after the first 26 weeks.
 **Participants will be asked to complete questionnaires monthly after CGM Initiation. A final questionnaire will be elicited at the earlier of CGM discontinuation or completion of study follow up (~52 weeks).
 ***HbA1c checks prior to unblinded CGM initiation, and at 3-month intervals following CGM initiation (~13 weeks, 26 weeks, 39 weeks, and 52 weeks)
[†]Follow up may be via phone, text, virtual (i.e. Skype), or app. outside of scheduled training. Additional follow up may be conducted as needed. Participants may follow up with study team as needed.
^{††}CGM supplied for blinded data collection will be provided. CGM supplies for six months of unblinded use will be provided for those who successfully complete blinded data collection.

3 Statistical Hypotheses

There are no primary outcomes and additional analyses not pre-specified here may be performed. In this study, we expect that most hypothesis testing will involve testing whether the change from baseline for various outcomes is significantly different from zero. This will primarily be for the CGM metrics, HbA1c, and the questionnaires. In those cases, the null hypothesis of the change from baseline being equal to zero will be tested against the alternative hypothesis that the change from baseline is nonzero. Analyses will be stratified by type of diabetes.

4 Sample Size

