- 59 • HbA1c, questionnaires, insulin, and other analyses will include all subjects with any
 60 amount of corresponding data following CGM initiation.
- 61 • The tabulations of the safety outcomes will include all participants who enrolled,
 62 regardless of how much data is available.

63 **7 Analysis of Study Endpoints**

64 **7.1 Calculation of CGM Metrics**

65 **7.1.1 Calculation of 13 Week CGM Metrics**

66 All CGM metrics listed in Section 5 will be calculated on a 13-week period for each subject
 67 level. The windows for the 13-week periods are defined as follows:

Time Point	Window
1-13 Weeks	0 to 91 days after the CGM initiation date
14-26 Weeks	92 to 183 days after the CGM initiation date
27-39 Weeks	184 to 274 days after the CGM initiation date
40-52 Weeks	275 to 365 days after the CGM initiation date

68
 69 For each 13-week period, CGM metrics will be calculated by pooling all CGM readings
 70 occurring from 12:00 AM on the first day of the 13-week period up until 11:59PM on the last
 71 day of the 13-week period. For the first 13-week period, the first CGM reading will be the start
 72 datetime of the period. If a participant discontinues CGM prior to the last day of the 13-week
 73 period, then CGM data will include readings up to the last CGM reading on the discontinuation
 74 date. Calibrations will be excluded from all these calculations. CGM metrics for 13-week periods
 75 with less than 168 hours of CGM data will be set to missing.

76 Baseline CGM metrics will be calculated by pooling all blinded CGM readings up to 90 days
77 prior to the date of CGM initiation for each subject. Baseline CGM metrics with less than 72
78 hours of CGM data will be set to missing.

79 The amount of time using the CGM will be calculated as the number of CGM values multiplied
80 by the expected CGM measurement frequency (i.e., 5min in general), with the exception that
81 there can only be one value within the CGM measurement frequency. Percentage of time CGM
82 is used will be calculated as the amount of time using the CGM divided by the total possible time
83 the participant could have used the CGM during the same period. Note that this denominator
84 includes sensor warm-up periods with no CGM values, so this metric will serve as a conservative
85 estimate of CGM use.

86 **7.1.2 Calculation of 4 Week CGM Metrics**

87 All CGM metrics listed in Section 5 also will be calculated on a 4-week interval for each subject.

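### SAP 7.4 names only a random subject effect and does not say whether visits are fitted jointly or singly; each reading can mislead on change from baseline

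*SAP*

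**What the plan says.** The model is given in one sentence of SAP 7.4: "For all outcomes, a linear mixed model with a random subject effect will be used to test" whether the mean change from baseline is zero. Protocol 6.5 says the same: "A linear mixed model with a random subject effect will be used to assess whether the change" from baseline differs from zero. Neither document names fixed effects, a residual covariance structure or a variance estimator.

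The models are to be fitted for each "of the subject level CGM metrics and HbA1c at 13, 26, 39, and 52 weeks", and for questionnaires at 26 and 52 weeks. This wording fits one model with all visits or a separate model for each visit. For inference, SAP 7.4 promises: "Point estimates and 95% confidence intervals for change in glycemic outcomes will be" reported. The tests are two-sided (SAP 3). SAP 12 uses the same model for p-values within subgroups.

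On missing data, SAP 7.3 says: "Missing data will not be imputed for any outcomes in this study and will be handled by means of" direct likelihood.

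The CGM definitions in SAP 7.1.1 differ between baseline and follow-up. Baseline pools blinded readings taken before CGM initiation, from what Protocol 2.7 describes as usually one sensor wear of about ten days: "Baseline CGM metrics with less than 72" hours of data are set to missing. Each follow-up value pools a 13-week window with a minimum of 168 hours.

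SAP 7.6 adds a complete-case paired t-test or Wilcoxon signed rank test for CGM and HbA1c outcomes.

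**The concern.** With independent residuals of constant variance (the usual software default, which the SAP does not state), a random subject effect is compound symmetry: equal variance at every visit and one correlation for every pair of visits. In a joint fit, the standard error of every change from baseline then comes from a single pooled within-subject variance. If the follow-up values resemble one another more than they resemble baseline, that pooled variance is too small for comparisons with baseline. The CGM definitions make this plausible: a few days before the intervention are compared with up to 13 weeks under it.

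Fitting each follow-up with baseline alone removes that problem but leaves the intermediate visits out of the likelihood. This matters because retention after week 26 may be selective. Study CGM supplies end at six months and participants must then seek insurance approval (Protocol 5.3). Extended follow-up is optional, needs an addendum consent and is offered to those who continue CGM (Protocol 2.1.1 and 3.1).

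At stake are the tests and 95% intervals for change from baseline, which are almost all of the planned inference in this single-arm study.

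**Working it through.** The documents give no SD, correlation, dropout rate or interval width, so there is no stated figure to reproduce. All values below are assumptions.

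**1. Joint fit, complete data.** There are five occasions: baseline and weeks 13, 26, 39 and 52. Per participant:

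- model variance of a change = 2 x (mean visit variance - mean between-visit covariance)
- true variance = V(baseline) + V(t) - 2 Cov(baseline, t)
- coverage = 2 Phi(1.96 x SE ratio) - 1, where the SE ratio is model SE divided by true SE

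Worked case with all SDs 1, baseline-to-follow-up correlation 0.6 and follow-up correlation 0.8. Ten pairs of visits give mean covariance (4 x 0.6 + 6 x 0.8)/10 = 0.72. Model variance is 2 x (1 - 0.72) = 0.56 and true variance is 2 - 2 x 0.6 = 0.80. The SE ratio is sqrt(0.56/0.80) = 0.84, so coverage is 89.9%.

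The ends of the assumed range (baseline-to-follow-up correlation 0.5-0.7, follow-up correlation 0.8-0.9, baseline SD 1.0-1.2 times follow-up SD):

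- Mildest (0.7, 0.8, equal SDs): model 2 x (1 - 0.76) = 0.48, true 0.60, ratio 0.89, coverage 92%.
- Strongest (0.5, 0.9, SD ratio 1.2): mean variance (1.44 + 4)/5 = 1.088; mean covariance (4 x 0.6 + 6 x 0.9)/10 = 0.78; model 2 x 0.308 = 0.616; true 1.44 + 1 - 1.2 = 1.24; ratio 0.70, coverage 83%.

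The type I error is therefore about 8-17% instead of 5%.

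**2. Other patterns, same formulas.**

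| Assumed pattern | SE ratio | Coverage |
|---|---|---|
| True compound symmetry | 1.00 | 95.0% |
| Equal SDs, correlations 0.7 (baseline) and 0.75 (follow-up) | 0.95 | 93.7% |
| SD 1.0 at baseline, 1.3 after; correlations 0.7 and 0.6 | 1.15 | 97.6% |
| Serial decay, AR(1) 0.8: week 13 | 1.31 | 99.0% |
| Serial decay: week 26 | 0.98 | 94.5% |
| Serial decay: week 39 | 0.84 | 90.0% |
| Serial decay: week 52 | 0.76 | 86.6% |

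**3. One follow-up with baseline, complete data.** With two occasions, the model variance is V(baseline) + V(t) - 2 Cov(baseline, t), which is the true variance. The ratio is 1.00 in every pattern, even with unequal variances, and the standard error equals that of the paired t-test.

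**4. Simulation check.** REML random-intercept fits, 52-week change, n = 200 (300 participants less the ceiling of 100 with type 2 diabetes), 300 replicates. The scenarios were SD 1.5 falling to 1.1 with correlations 0.5 and 0.8, and equal SDs with correlations 0.6 and 0.8.

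- Joint fit: coverage 84.0% and 87.7% without dropout, 89.3% and 92.0% with 30% random monotone dropout.
- Per-visit fits: 94.3% to 96.7%, including a compound-symmetry scenario and both dropout settings.
- Monte Carlo error is about 1.3 points near 95% and 2 points near 85%.

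**5. What per-visit fitting costs under dropout.** Correlations 0.6 and 0.85, equal SDs.

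- *Precision, 30% random dropout.* The relative SE is about 0.95 for the joint unstructured model, 1.04 per visit and 1.07 for complete cases. The per-visit SE is about 10% larger than the joint one (1.04/0.95).
- *Bias, 30% dropout after week 26.* Dropout is made more likely by worse week-26 values (logit slope 0.5 to 1.5 per SD), and the true 52-week change is -0.40 SD. The joint unstructured model gives -0.40, the per-visit model -0.47 to -0.57, and complete cases -0.44 to -0.48. The per-visit model overstates the change by 0.07 to 0.17 SD.

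**The case against.** The strongest reply is that the SAP does not specify the model that produces narrow intervals. Fitted per visit, the standard errors are right on complete data and stay close to nominal under random dropout. A baseline-plus-one-visit likelihood is still direct likelihood and still uses participants who have only a baseline. A joint fit to change scores, another possible reading, would also give correct standard errors if the follow-up visits are interchangeable. All of this stands. The SAP leaves the choice open, and the size of any error depends on it.

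A reader might infer that the intervals are too narrow whatever is done. The documents do not support that. The direction depends on the unstated covariance: under serial decay the week-13 interval is too wide while those at weeks 39 and 52 are too narrow.

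A reader might also extend the measurement argument to HbA1c. That does not follow. HbA1c comes from the same kind of mailed fingerstick sample, measured at a central laboratory, at baseline and at every follow-up (Protocol 2.5.1 and 3.6.1). Only differing responses to the intervention could weaken its baseline correlation.

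SAP 7.6 is a real safeguard. Its paired t-test does not assume compound symmetry, so a materially narrow joint-model interval would show beside it. But it is a sensitivity analysis, uses complete cases only (and so shares the dropout bias), and omits the questionnaires.

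Finally, the SAP calls all analyses exploratory, names no primary outcome and describes a convenience sample. This limits the consequence but does not remove the promise of tests and intervals.

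**Conclusion.** The point holds as an under-specified model with a conditional consequence. In a joint fit with default residuals, intervals for CGM changes are plausibly too narrow, with coverage of about 83-92% under the assumed correlations and SDs; other covariance patterns give little error or the opposite one. In per-visit fits, complete-data standard errors are correct. The cost there is about 10% in standard error under 30% random dropout, and a possible bias of 0.07-0.17 SD if late dropout depends on week-26 values as assumed.

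It would be too strong to say that per-visit fitting defeats the missing-data method of SAP 7.3. It remains a likelihood analysis, and bias arises only if dropout depends on the values it leaves out. Neither reading does as well as a joint unstructured model. Severity is modest: it should be corrected, but no confirmatory conclusion depends on it.

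**What to change.** In SAP 7.4 and Protocol 6.5, specify one joint model per outcome and diabetes type:

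- Response: baseline and all modelled follow-up values (13, 26, 39 and 52 weeks for CGM metrics and HbA1c; 26 and 52 weeks for the questionnaires that are tested).
- Visit as a categorical fixed effect, with each change from baseline estimated as a contrast.
- Unstructured covariance: 5 x 6/2 = 15 parameters for five occasions, 3 x 4/2 = 6 for three.
- Fallback if the model fails to converge, for example in small SAP 12 subgroups: a named simpler structure with robust (sandwich) standard errors.

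This gives correct large-sample standard errors without assuming compound symmetry, and lets the direct-likelihood analysis in SAP 7.3 use the intermediate visits. Keep the SAP 7.6 paired tests as the sensitivity analysis. The cost is a change of wording; no new data are needed, and some intervals may be somewhat wider.
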